#### 12.2 Follow-up

#### Longitudinal observational study

The follow up period is 12 months, in line with the timeline for routine annual Enroll-HD assessments.

# Nested RCT

The follow up period is 12 months, in line with the timeline for routine annual Enroll-HD assessments.

# 13 Safety Reporting

The Principal Investigator is responsible for ensuring that all site staff involved in this trial are familiar with the content of this section. All SAEs must be reported immediately (and within 24 hours of knowledge of the event) by the PI at the participating site to the PACE HD Trial Manager unless the SAE is specified as not requiring immediate reporting (see section 13.2).

#### 13.1 Definitions

Table 4: Adverse event definitions

Term	Definition
Adverse Event (AE)	Any untoward medical occurrence in a participant or clinical trial participant administered a medicinal product and which are not necessarily caused by or related to that product
Serious Adverse Event (SAE)	Any adverse event that -  Results in death  Is life-threatening*  Required hospitalisation or prolongation of existing hospitalisation**  Results in persistent or significant disability or incapacity  Consists of a congenital anomaly or birth defect  Other medically important condition***

\*Note: The term 'life-threatening' in the definition of serious refers to an event in which the trial participant was at risk of death at the time of the event or it is suspected that used or continued used of the product would result in the subject's death; it does not refer to an event which hypothetically might have caused death if it were more severe.

- \*\* **Note:** Hospitalisation is defined as an inpatient admission, regardless of the length of stay, even if the hospitalisation is a precautionary measure for continued observation. Pre-planned hospitalisation e.g. for pre-existing conditions which have not worsened, or elective procedures, does not constitute an SAE.
- \*\*\* **Note:** other events that may not result in death, are not life-threatening, or do not require hospitalisation, may be considered as an SAE when, based upon appropriate medical judgement, the event may jeopardise the participant and may require medical or surgical intervention to prevent one of the outcomes listed above.

# 13.2 Trial Specific SAE Reporting requirements

We will only record AEs for the participants taking part in the nested RCT. The proposed interventions are not expected to result in any adverse events. The physical activity intervention does not specifically involve any heavy load-bearing exercise or heavy eccentric muscle activity. However, some minor muscle soreness or muscular strain may occur in the few days following the initiation of a new exercise program or increase physical activity. This would normally resolve spontaneously and would not require any specific interventions or additional medical care, but will be noted as a potential expected related AE if reported.

Falls are an expected AE as part of the clinical condition particularly in the mid-stages of the disease. Any falls will be recorded routinely by the research team and those that result in hospitalisation (thus deemed to be an SAE) will be assessed for causality by the site PI and notified to the trial team.

# 13.3 Causality

The Principal Investigator (or another delegated suitably qualified clinician or therapist from the trial team registered on the delegation log) will assess each SAE to determine the causal relationship and the Chief Investigator (or another suitably qualified therapist from the Trial Management Group) can also provide this assessment where necessary. Causal relationship will be assessed for the 12-month physical activity intervention.

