# Nested RCT

Participants will be assessed at baseline, 6 months and 12 months.

Table 1: Assessments additional to the standard Enroll-HD test battery for all sites:

Construct	Measure	Time to complete	Time points
Fitness	Predicted VO2 Max will be measured during stepwise incremental exercise test  . The test is performed on a cycle ergometer with participants seated in a standardized position. Participants will attempt to maintain a cadence of 50 revolutions per minute (rpm), starting at 50 Watts and increasing by 25	20 min	Baseline, 6 months (RCT only), 12 months

	Watts every two minutes until test termination. The test will be terminated when the participant reaches volitional exhaustion or cadence drops by 10 rpm. At the end of each increment, work-rate (Watts), rating of perceived exertion (Borg RPE scale) and heart rate will be recorded for analysis and conversion to predicted VO2 max score.		
Walking endurance	The 6-minute walk test will be used as a measure of walking endurance. This test evaluates the distance walked over a 6 minute period, and has been validated for use in HD  .	10 min	Baseline, 6 months (RCT only) and 12 months
Patient- reported clinical symptoms	HD Pro-Triad  will be used to assess disease specific symptoms including cognitive decline, emotional/behavioural dyscontrol and motor dysfunction.	10 min	Baseline and 12 months
Physical Activity Monitoring	Brunel Lifestyle Physical Activity Questionnaire  self-report instrument that measures the planned and unplanned dimensions of lifestyle physical activity.	5 minutes	Baseline
	Research-grade physical activity monitors (Gene-activs) will be used for a 7-day physical activity assessment .  Participants will be given the monitors at the consent visit, and will be asked to return them at the baseline visit one week later. They will be requested to wear them for 24 hours a day for the full week, except when showering. Participants will be given the monitors at the end of the assessments, and will be given addressed stamped mailing envelopes to return the monitors one-week later. Data obtained for analysis will include level of overall physical activity, sedentary behavior and sleep patterns. For validation of sleep time compared to sedentary time, participants will be asked to complete and return sleep diaries for the 7 day period of physical activity assessment.	5 min	Baseline, 6 months (RCT only) and 12 months

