**Table 5: Assessment of Causality** 

Relationship	Description	Reasonable possibility that the SAE may have been caused by the intervention?
Unrelated	There is no evidence of any causal relationship with the trial/intervention	No
Unlikely	There is little evidence to suggest there is a causal relationship with the trial/intervention (e.g. the event did not occur within a reasonable time after administration of the trial medication). There is another reasonable explanation for the event (e.g. the participant's clinical condition, other concomitant treatment).	No .
Possible	There is some evidence to suggest a causal relationship with the trial/intervention (e.g. because the event occurs within a reasonable time after administration of the trial medication). However, the influence of other factors may have contributed to the event (e.g. the participant's clinical condition, other concomitant treatments).	Yes
Probable	There is evidence to suggest a causal relationship and the influence of other factors is unlikely.	Yes
Definite	There is clear evidence to suggest a causal relationship and other possible contributing factors can be ruled out.	Yes

The causality assessment given by the Principal Investigator (or delegate) cannot be downgraded by the Chief Investigator (or delegate), and in the case of disagreement both opinions will be provided.

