# Serious Adverse Event (SAE) Reporting

Trial Database: https://pacehd.sewtudb.cf.ac.uk/login/

email address: [contact]

Serious adverse events should be reported from the time of the baseline assessment, throughout the intervention period. SAEs do not need to be reported if they occur during the week long follow up period of activity monitoring.

An SAE form is not considered as complete unless the following details are provided:

- Full participant trial number
- An Adverse Event
- A completed assessment of the seriousness, and causality as performed by the PI ( or another suitably qualified clinician or therapist from the site trial-team registered on the delegation log).

If any of these details are missing, the site will be contacted and the information must be provided by the site to the CTR within 24 hours. All other AEs should be reported in the adverse event reporting section of the database following the eCRF procedure described in Section 16.

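### Section 13.3 and the Table 5 heading tie SAE causality to the intervention, three Table 5 rows tie it to the trial or intervention, and neither reading correctly attributes an SAE provoked by a trial assessment

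*Protocol*

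**What the plan says.** The protocol names the object of the causality judgement in three places.

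- Section 13.3, text: "Causal relationship will be assessed for the 12-month physical activity intervention".
- Section 13.3, Table 5, heading of the Yes/No column: "Reasonable possibility that the SAE may have been caused by the intervention".
- Section 13.3, Table 5, row descriptions: Unrelated reads "There is no evidence of any causal relationship with the trial/intervention" and Possible begins "There is some evidence to suggest a causal relationship with the trial/intervention". Unlikely uses the same wider object. Probable and Definite name no object.

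Section 13.4.1 sets the reporting window: "Serious adverse events should be reported from the time of the baseline assessment, throughout the intervention period". Section 13.2 limits the population: "We will only record AEs for the participants taking part in the nested RCT".

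Table 1 in section 12.1 lists the incremental cycle ergometer test as an assessment, separate from the intervention described in section 11.1. Its end point is stated as "The test will be terminated when the participant reaches volitional exhaustion or cadence drops by 10 rpm" and its time points as "Baseline, 6 months (RCT only), 12 months". Section 11.3 states that controls in the nested RCT do not receive the intervention.

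**The concern.** SAEs are collected in people who have had no exposure to the one cause that section 13.3 names, and those people undergo a demanding research test while the reporting window is open. The form needs an answer for an SAE provoked by that test, and the protocol gives two incompatible instructions for reaching it.

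At stake is what the trial can say about the source of risk. Safety is among the primary feasibility outcomes in the Synopsis, and section 15.1 has it summarised for the RCT. A later trial will want to know whether serious events came from the coaching programme or from the testing. Site staff make the attribution when they report the event (sections 13.3 and 13.4.1), so an analysis plan could not reliably recover a distinction that was never recorded.

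**Working it through.** The protocol states no figure to reproduce. The check is a comparison of the two readings, followed by a count.

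**Step 1: the two readings**

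Take an SAE provoked by the cycle test.

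| Who and when | Narrow reading (13.3 text and Table 5 heading) | Wider reading (Unrelated, Unlikely and Possible rows) |
|---|---|---|
| RCT control, any visit | No: the intervention was never received | Possible or higher, which maps to Yes under a heading that asks about the intervention |
| Intervention arm, baseline | No: the intervention has not started | The same Yes, for an intervention not yet received |
| Intervention arm, 6 or 12 months | Yes or No, according to whether the assessor suspects the programme; the test has no place in the answer | Yes, without saying whether test or programme |

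In the first two rows the narrow reading leaves the trial's own procedure out of the record, and the wider reading names the wrong cause. In the third row a single rating cannot separate the two candidate causes. Two sites, each following part of section 13.3 faithfully, could code the same event in opposite ways.

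**Step 2: how many planned tests fall in the first two rows**

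Inputs: RCT control arm 30 and intervention arm 30 (section 12); three test time points in the RCT (Table 1). Assumptions: full attendance, and the baseline test precedes the first coaching session.

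- All planned RCT tests: (30 + 30) × 3 = 180.
- Control-arm tests: 30 × 3 = 90.
- Intervention-arm baseline tests: 30 × 1 = 30.
- Tests without prior intervention exposure: 90 + 30 = 120.
- Share: 120 / 180 = 67%.

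**Step 3: sensitivity to the reporting window**

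The window runs through the intervention period, so the 12-month test sits at its edge. With the 12-month tests left out:

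- All tests: 60 × 2 = 120.
- Without prior exposure: 30 × 2 + 30 = 90.
- Share: 90 / 120 = 75%.

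The observational cohort would add 60 × 2 = 120 tests. No AEs are recorded there, so no causality rating arises and those tests are outside this point.

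**The case against.** The strongest reply is that Table 5 already admits trial procedures. An assessor chooses a row by its description, and the Yes or No follows from the row. A cycle-test SAE in a control does not fit the Unrelated description, so it can be rated Possible or higher. A reader might infer from section 13.3 alone that every such event has to be classed as not related. The documents do not support that, because a text that says two things does not force one of them. This part of the reply stands. It does not rescue the rule, because the resulting Yes sits under a heading that attributes the event to an intervention the person had not received.

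Two further replies also stand.

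- **The event is not lost.** SAEs are sent to the trial team within 24 hours, evaluated centrally, followed up to resolution where possible, and can go to the management group and the steering committee. The site's rating cannot be downgraded. RCT participants pass a safety screen first. The event date and narrative might also point to the test, but the SAE form is not shown and section 13.4.1 lists only its minimum content.
- **The count of SAEs by arm does not depend on the label.** Both arms take the same test at the same times, and no formal hypothesis testing is planned. A reader might infer that mislabelled control events would inflate a background rate against which the intervention arm is judged. The protocol describes no such comparison. Section 5.3 defines the safety outcome through monthly therapist records of falls, medication changes, service use and admissions, with no causality rating in it.

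**Conclusion.** The concern holds as an inconsistency with consequences. Section 13.3 and the Table 5 heading name the intervention, while three Table 5 rows name the trial or the intervention. On either reading, an SAE provoked by a trial assessment in an RCT control, or at baseline in either RCT arm, gets an incomplete or wrong attribution. In the intervention arm at 6 and 12 months it cannot be split between test and programme.

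The 120 of 180 (67%; 75% without the 12-month visit) shows how much of the planned testing falls where the intervention cannot be the cause. It should not be read as a misclassification rate. The protocol gives no SAE rate for the test, so the number of affected events cannot be derived and may be small. With 30 per arm, though, a single differently coded event would visibly change the account of related SAEs.

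The conclusion concerns the nested RCT only. It rests on the protocol wording and assumes that the SAE form, which is not shown, follows section 13.3 and Table 5.

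**What to change.** Reconcile the passages so that the section 13.3 sentence, the Table 5 column heading and all five row descriptions name the same object. Have the assessor rate relatedness separately for (a) the 12-month physical activity intervention and (b) trial procedures, including the incremental cycle test and the 6-minute walk test, in both RCT arms. Add one field to the SAE form to hold the second rating, and summarise related SAEs by source and arm.

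The cost is one sentence, one heading, an edit to the row wording and one form field, with no extra visits, staff or participants. The downside is that a few more events will be labelled as related to the trial.

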**Table 5: Assessment of Causality** 

Relationship	Description	Reasonable possibility that the SAE may have been caused by the intervention?
Unrelated	There is no evidence of any causal relationship with the trial/intervention	No
Unlikely	There is little evidence to suggest there is a causal relationship with the trial/intervention (e.g. the event did not occur within a reasonable time after administration of the trial medication). There is another reasonable explanation for the event (e.g. the participant's clinical condition, other concomitant treatment).	No .
Possible	There is some evidence to suggest a causal relationship with the trial/intervention (e.g. because the event occurs within a reasonable time after administration of the trial medication). However, the influence of other factors may have contributed to the event (e.g. the participant's clinical condition, other concomitant treatments).	Yes
Probable	There is evidence to suggest a causal relationship and the influence of other factors is unlikely.	Yes
Definite	There is clear evidence to suggest a causal relationship and other possible contributing factors can be ruled out.	Yes

The causality assessment given by the Principal Investigator (or delegate) cannot be downgraded by the Chief Investigator (or delegate), and in the case of disagreement both opinions will be provided.

# 13.4 Reporting procedures

# 13.4.1 Participating Site Responsibilities

The PI (or delegated suitably qualified clinician or therapist from the site trial team registered on the delegation log) should complete the safety reporting form in the trial database to acknowledge that he/she has performed the seriousness and causality assessments. Investigators should also report SAEs to their own local authorities in accordance with local practice.

A completed SAE form for all events requiring immediate reporting should be submitted via the trial database or completed on a paper form and emailed to the CTR within 24 hours of knowledge of the event, if the database is unavailable. Submission of the form via the trial database will generate an automatic alert to the trial team. A separate form must be used to report each event, irrespective of whether or not the events had the same date of onset.

The participant will be identified only by HDID and trial PID. The participant's name should not be used on any correspondence.

It is also required that sites respond to and clarify any queries raised on any reported SAEs and report any additional information as and when it becomes available through to the resolution of the event. Additionally, the CTR may request additional information relating to any SAEs and the site should provide as much information as is available to them in order to resolve these queries.

# Serious Adverse Event (SAE) Reporting

Trial Database: https://pacehd.sewtudb.cf.ac.uk/login/

email address: [contact]

Serious adverse events should be reported from the time of the baseline assessment, throughout the intervention period. SAEs do not need to be reported if they occur during the week long follow up period of activity monitoring.

An SAE form is not considered as complete unless the following details are provided:

- Full participant trial number
- An Adverse Event
- A completed assessment of the seriousness, and causality as performed by the PI ( or another suitably qualified clinician or therapist from the site trial-team registered on the delegation log).

If any of these details are missing, the site will be contacted and the information must be provided by the site to the CTR within 24 hours. All other AEs should be reported in the adverse event reporting section of the database following the eCRF procedure described in Section 16.

#### 13.4.2 The CTR Responsibilities

Following the initial report, all SAEs should be followed up to resolution wherever possible, and further information may be requested by the CTR. Follow up information must be provided on a new SAE form. The CTR should continue reporting SAEs until the participant receives the last part of the intervention. Once an SAE is received at the CTR, it will be evaluated by staff at the CTR and sent to the Chief Investigator (or their delegate) for an assessment of expectedness.

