# 5.3 Primary outcomes measure(s)

The primary outcome measures for this trial are focused on feasibility of the 12-month physical activity intervention.

- Recruitment rate will be assessed using site recruitment logs.
- Retention rate will be measured as the percentage of individuals who completed the intervention.
- Adherence rates will be defined as percentage of intervention sessions completed,
- Safety will be assessed through monthly documentation completed by therapists administering the intervention, which captures information on falls history, medication

changes, healthcare service use and hospital admissions (classified as serious adverse events).

- Fidelity of the interventions will be assessed via review of coach documentation and activity monitor data.
- Data completeness will be assessed by the percentage of data entered into the database.

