# 11.3 Intervention comparator

#### Nested RCT

Those participants in the nested RCT randomised to activity as usual will not receive the physical activity intervention and will be asked to continue with their usual level of physical activity for the 12 month follow up period. They will not receive home visits from the intervention delivery staff (physical therapists), but they will be asked to record their activity monthly in paper diaries which will be sent to them. These participants will also receive monthly prompts via their preferred method of communication (e-mail/ telephone/ text messaging) to remind them to complete and return the diaries to their local coordinating centre in the stamped, addressed envelope provided. Their activity will not be monitored with the use of devices outside the week long activity monitoring period using Gene-activ devices that all participants will undertake.

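### The end of the SAE reporting window is inconsistently defined: one rule cannot apply to controls and, read literally, closes early for participants who stop the intervention

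*Protocol*

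**What the plan says.** Safety is one of the primary feasibility outcomes. Several parts of the protocol bear on how long, and by whom, serious events are captured.

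- **Section 13.4.2 (trials unit):** "The CTR should continue reporting SAEs until the participant receives the last part of the intervention".
- **Section 13.4.1 (sites):** "Serious adverse events should be reported from the time of the baseline assessment, throughout the intervention period". The only stated exclusion is the final accelerometer week: "SAEs do not need to be reported if they occur during the week long follow up period of activity monitoring".
- **Section 13.2 (population):** "We will only record AEs for the participants taking part in the nested RCT", that is, both arms.
- **Section 11.3 (control arm):** participants "randomised to activity as usual will not receive the physical activity intervention" and have no home visits from the therapists.
- **Section 5.3 (source):** "Safety will be assessed through monthly documentation completed by therapists administering the intervention". The items captured include "healthcare service use and hospital admissions (classified as serious adverse events".
- **Section 13.1 (definition):** for pre-planned admissions and those for "elective procedures, does not constitute an SAE".
- **Section 10.2:** an RCT participant who misses more than four coaching contacts in a row counts as lost, and the team then stops trying to reach that person.
- **Section 10.1:** falls or worsening health may lead to stopping the intervention. Safety data at withdrawal are mentioned only for an event already in progress.
- **Table 3:** adverse event assessments are marked to Month 12 under the intervention heading, and a telephone Health and Falls review is marked for both arms into months 7-12. The usual-care rows are only partly legible in the text available.

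**The concern.** The end-point in 13.4.2 is tied to one person's receipt of the intervention, not to the calendar. That matters in three ways. Controls have no last part of an intervention, so the rule gives no answer for them. Intervention participants who stop early have no stated SAE reporting afterwards, and because stopping may follow falls or deterioration, the missing time need not be a random sample of follow-up. Finally, the source named in 5.3 exists in one arm only.

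Safety is a listed primary outcome, the trial is unblinded (14.2) and no data monitoring committee is convened (22.3). The SAE summaries therefore carry much of the safety evidence for any larger trial. If sites and the trials unit follow different sentences, those summaries will rest on different windows in different people.

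**Working it through.** **1. The protocol's own figure.** None is given for safety. The only design figure is the ±8.2% half-width for 70% retention with n = 120 (14.3). It reproduces: 1.96 × √(0.7 × 0.3 / 120) = 0.082. The present point does not depend on it.

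**2. Which window applies to whom.**

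| Participant | 13.4.2 read literally | 13.4.1 with a 12-month period, and Table 3 |
|---|---|---|
| Intervention, completes | about month 12 | about month 12 |
| Intervention, stops at month t | month t | about month 12 |
| Control | no end-point | about month 12 |

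The two readings agree only in the first row. Section 10.2 supports the left column for intervention participants who miss coaching; controls have no coaching sessions and cannot trigger that rule.

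**3. What the literal rule could cost (illustration).** Inputs: 30 intervention participants (section 6) and 12 months, so 30 × 12 = 360 person-months. The stopping shares d of 30%, 40% and 60% are borrowed from the drop-out thresholds in 15.1. The stopping month t is assumed, because the protocol gives none.

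Observed person-months = 360 × [1 − d(12 − t)/12]

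| d | t = 3 | t = 6 | t = 9 |
|---|---|---|---|
| 30% | 279 (22.5% lost) | 306 (15% lost) | 333 (7.5% lost) |
| 40% | 252 (30% lost) | 288 (20% lost) | 324 (10% lost) |
| 60% | 198 (45% lost) | 252 (30% lost) | 306 (15% lost) |

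For d = 30% and t = 6: 9 people × 6 months = 54 lost, and 360 − 54 = 306.

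**4. Which summaries are affected.** Suppose the event rate after stopping is k times the rate before (k assumed). With t = 6, the share of events missed is 0.5kd / [(1 − d) + 0.5d + 0.5kd].

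- d = 30%: k = 1 gives 0.15/1.00 = 15%; k = 2 gives 0.30/1.15 = 26%; k = 3 gives 0.45/1.30 = 35%.
- d = 60%: k = 1 gives 0.30/1.00 = 30%; k = 2 gives 0.60/1.30 = 46%; k = 3 gives 0.90/1.60 = 56%.

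With k = 1, a rate per observed person-month is unbiased; only counts and proportions per randomised participant are too low. With k above 1, the rate is too low as well. At d = 30% and k = 2 the full-window rate is 1.15 times the observed one, so the observed rate is 1 − 1/1.15 = 13% too low.

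**The case against.** The strongest reply is that 13.4.2 describes what the trials unit does, while the site window is in 13.4.1. The period named there reads naturally as the fixed 12-month phase: the synopsis gives a 12-month intervention duration, and section 18 describes an intervention phase followed by a monitoring week. An explicit exclusion of that week would make little sense if each person's window closed at the last session attended. Table 3 schedules safety contact late into the year in both arms, and Table 6 lists the Health and Falls Record for the RCT as a whole. Section 10.1 separates leaving the intervention from leaving data collection, and section 9.4 keeps participants given alternative treatment in follow-up. Linked Enroll-HD event data at Month 12 cover all sites. Safety is only to be summarised (15.1), and formal testing is ruled out (14.3).

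Most of this stands. A reader might infer from 13.4.2 that early stoppers and controls leave all safety surveillance, or that the safety outcome is already shown to be biased. The documents support neither. They show a 12-month intention in some places and a different rule in another.

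What the reply does not do is remove the conflict. A 12-month reading of 13.4.1 contradicts 13.4.2 and sits badly with 10.2. Month-12 linked data may recover some events but are no substitute for the 24-hour reporting route. Descriptive summaries also need equal windows if the arms are to be set side by side.

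The hospital-admission wording in 5.3 may be shorthand for the 13.1 definition. It is a separate, smaller inconsistency that would change counts if applied as written.

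**Conclusion.** The point holds as an inconsistency in a rule that the protocol itself fixes. The end of the SAE window is undefined for controls under 13.4.2, falls early for intervention participants who stop if that sentence is followed, and is about 12 months under the natural reading of 13.4.1 and Table 3.

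If the 13.4.2 rule is followed, SAE counts and proportions per randomised participant may be too low in the intervention arm and not comparable with control. The direction is a risk, not an established bias, and the size cannot be derived from the protocol. The figure of 306 of 360 person-months assumes 30% stopping, all at month 6, and no capture afterwards. Whether a person-time rate is also distorted depends on the event rate after stopping, which is not given. The correction is cheap and should be made, because safety is a primary outcome.

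**What to change.** Reconcile 5.3, 10.2, 13.4.1, 13.4.2 and Table 3 as follows.

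- **One window.** SAEs are reported for every randomised participant in both arms from the baseline assessment to the month-12 assessment, whether or not the intervention is still received, unless the participant withdraws from data collection. Starting at baseline keeps the start now in 13.4.1 and covers the baseline exercise test, which may precede randomisation because the baseline motor score is a minimisation factor. The exclusion of the final monitoring week can stay.
- **One source.** Name the Health and Falls Record, taken monthly in both arms, as the basis for between-arm safety summaries. Use linked Enroll-HD Month-12 event data for those lost to follow-up. List events found only at coaching visits separately.
- **Denominator.** Report observed person-time by arm alongside counts.
- **Definition.** In 5.3, refer to the SAE definition in 13.1 instead of classing every hospital admission as serious.

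The cost is a protocol amendment, some further telephone reviews for early stoppers, and a change to the 10.2 wording that ends attempts at contact. Table 3 does not state the interval of the usual-care reviews; if it is not already monthly, some control-arm calls are added.
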